### *Rationale for study population:*

In this study, as in our initial study, we will enroll only obese women without diabetes. Certainly obesity is not a disease limited to women, but we have chosen to enroll only women because we do not wish to examine differences in the mechanisms and rate of weight loss between men and women. In addition, differences in body fat distribution between men and women may affect timing, duration, and amount of weight loss, which would introduce additional variability in our data. Future studies addressing weight loss among obese men treated with exenatide and/or studies comparing men and women treated with exenatide may follow from this study. By excluding women with diabetes, we aim to minimize the presence of co-morbidities associated with diabetes and insulin resistance that may mitigate the effects of exenatide on energy expenditure and serum

metabolic parameters.

[figure not shown]
### B3. DESCRIPTION OF RESEARCH PROTOCOL

#### A. Study Design – Overview, Methods, Procedures

##### Overview

We propose a 52-week randomized, placebo-controlled, single-blind interventional study. Eligible subjects will be randomized in a 2:1 distribution to exenatide or placebo treatment. Subjects in the placebo treatment group will be given specific dietary counseling and meal plans aimed at achieving at least 5% weight loss (approximately 500-1000 cal/day caloric reduction). Subjects in the exenatide treatment group will be advised to follow a eucaloric diet and will not be given a diet plan. Subjects will be blinded to their treatment arm but investigators will not.

[figure not shown]
All subjects will receive twice daily treatment for 12 weeks. Subjects will inject 5 mcg exenatide or placebo twice a day for the first 2 weeks and then 10 mcg twice a day for the remainder of the study. We will identify subjects who lose  $\geq 5\%$  body weight at 12 weeks as *high responders* to exenatide or placebo, and such subjects will remain in the study for 52 weeks with monthly study visits. Subjects who lose  $< 5\%$  body weight at 12 weeks will be considered *nonresponders* and will discontinue participation after 12 weeks. At 24 weeks, subjects in the placebo group who have not lost 10% of their body weight will discontinue participation. At 52 weeks, high responders in both treatment groups will discontinue treatment. Subjects will return at 3 and 6 months for post-treatment followup visits. All visits are outpatient visits that will take place in the Beth Israel Deaconess Medical Center Clinical Research Center. A figure outlining the study design to date is provided below.

[figure not shown]
##### Rationale for study design:

Subjects are randomized to exenatide treatment with general dietary counseling or placebo treatment with aggressive dietary intervention. We are including placebo treatment with aggressive dietary intervention in order to minimize potentially unequal dropout rates in the exenatide versus dietary intervention arms. We will not be able to achieve our primary objectives without an adequate control group that loses at least 5% of body weight with dietary intervention alone.

As of 7/1/14, using a 3:1 randomization scheme, we have enrolled 84 subjects in the exenatide group and 28 in placebo. Due to a higher-than-expected exenatide high responder rate (approximately 60% compared to our prediction of 30%), we must change our randomization scheme to 1:1 to enroll enough subjects in the placebo group for comparison. The number of subjects screened will also be increased from 250 to 300 to achieve our enrollment goal of 250. Thus, we will screen 148 more subjects for a total of 300 screened.

As of 6/5/15, using a 1:1 randomization scheme, we enrolled 24 subjects in the exenatide group and 10 in placebo. Due to a higher than expected drop out rate in the exenatide group and a high response rate in the placebo group, we will change our randomization scheme to 2:1 to enroll enough subjects in both groups for comparison based on our original power calculation. The following figure outlines the new changes:

The placebo arm will be used to study weight-loss induced metabolic changes that are independent of exenatide. Because the subjects in the placebo/dietary intervention arm serve as a weight-loss comparison group, these subjects will be dropped from the study at 12 weeks if they do not lose 5% of their body weight. Subjects in the exenatide treatment arm will be characterized as “non-responders” (<5% weight loss) or “responders” (≥5% weight loss) based on weight loss at 12 weeks. Data from our previous exenatide study in non-diabetic obese women shows that 12 weeks provides a reasonable timeframe to differentiate “non-responders” and “responders.” Because this study focuses only on the characteristics of exenatide responders, subjects in the exenatide treatment arm with less than 5% weight loss at 12 weeks will be dropped from the study. Exenatide “responders” will continue treatment for 52 weeks to assess the magnitude and duration of weight loss in this subgroup. These subjects will also participate in 3-month and 6-month follow-up visits to assess weight changes post-treatment. Subjects in the dietary intervention arm will continue study participation for up to 52 weeks if they demonstrate ongoing weight loss and then attend 3-month and 6-month follow-up visits after returning to *ad-lib* eating.

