#### *Outcome measurements:*

*Weight:* We will compare the duration and magnitude of weight loss among exenatide responders with the

duration and magnitude of weight loss among subjects assigned to placebo with a calorie-restricted diet over 52 weeks. We will also compare changes in weight at 3 and 6 months after the cessation of exenatide treatment or diet. Weight loss will be correlated to baseline BMI.

**Body composition:** Baseline body composition may predict response to exenatide treatment, and weight loss with exenatide may be associated with decreased fat versus lean body mass compared to diet-induced weight loss. We will compare the effect of exenatide treatment versus caloric reduction on body composition over 52 weeks using bioelectrical impedance analysis (BIA) and by measuring waist circumference.

**Resting energy expenditure (REE):** Our initial data suggest that exenatide may blunt the decrease in resting energy expenditure that is typically associated with diet-induced weight loss. We will measure resting energy expenditure (REE) via indirect calorimetry at baseline, at weeks 12, 24, and 52, and after 5%, 10%, 15% weight loss is achieved, and at additional 5% weight loss timepoints, as applicable (i.e., 20%, 25%, etc).

**Mixed meal test:** Exenatide may improve beta cell function and lower postprandial triglycerides in nondiabetic individuals. Measurement of fasting insulin and triglyceride levels does not capture these effects. We will administer a mixed liquid meal (Boost) and measure serial postprandial insulin, , and triglyceride levels. Subjects will have a mixed meal test at baseline, and at weeks 12, 24, and 52.

**Thermic effect of food:** Exenatide treatment may result in an increase in the thermic effect of food, which could explain, at least in part, why we did not see a significant reduction in energy expenditure among exenatide high responders in our initial study. We will measure the thermic effect of food using indirect calorimetry following the mixed meal challenge. Energy expenditure will be measured for 15-20 minutes every hour for four hours after the mixed meal challenge. The thermic effect of food will be measured in a subset of subjects at baseline, and at weeks 12, 24, and 52.

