**Study duration:**

All subjects randomized to exenatide treatment will continue participation for 12 weeks. At 12 weeks, subjects who are high responders will continue participation for 52 weeks plus followup visits at 3 and 6 months. Exenatide high responders will remain in the study even if weight loss plateaus or if there is weight regain. Exenatide nonresponders will discontinue participation after 12 weeks.

Subjects in the placebo/diet intervention arm will discontinue participation if they fail to lose 5% of their body weight after 12 weeks or 10% of their body weight after 24 weeks. Subjects who demonstrate ongoing weight loss will continue placebo/dietary intervention for up to 52 weeks, plus follow-up visits at 3 and 6 months. Metabolic monitoring will occur when subjects have lost 5% and 10% of their body weight.

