- **Weeks 16 and 20 — Follow-up visits**
  - Standard measurements
  - Dietary counseling
  - VAS for nausea, satiety, hunger
  - 24-hr food recall
  - Assessment of symptoms, adverse events, and diet/medication compliance
  - If subject has attained 10%, 15%, or > 15% weight loss in a 5% increment, follow 10% weight loss procedures”
  - Urine pregnancy test for premenopausal women
  
- **Week 24 — Follow-up visit with safety labs; discontinue <10% weight loss on placebo**
  - Fasting safety labs (CBC, metabolic panel, transaminases, lipid panel, lipase)
  - Fasting leptin, soluble leptin receptor, insulin, cortisol, adiponectin, CRP, FGF21 levels
  - Physical exam
  - Standard measurements
  - Dietary counseling
  - VAS for nausea, satiety, hunger
  - 24-hr food recall
  - Assessment of symptoms, adverse events, and diet/medication compliance
  - Resting energy expenditure
  - Mixed meal test
  - Thermic effect of food (TEF) in subset of subjects
  - Subjects who have not lost 10% body weight on placebo treatment discontinue participation at 24 weeks
  - Physical activity monitoring in subjects continuing participation if device is available
  - Urine pregnancy test for premenopausal women
  
- **Weeks 28, 32, 36, 40, 44, 48 — Followup visits**
  - Standard measurements
  - Dietary counseling
  - VAS for nausea, satiety, hunger
  - 24-hr food recall
  - Assessment of symptoms, adverse events, and diet/medication compliance
  - If subject has attained 10%, 15%, or > 15% weight loss in a 5% increment, follow 10% weight loss procedures”
  - Urine pregnancy test for premenopausal women
  
- **Week — 52 Final Treatment visit**
  - **Discontinue exenatide treatment or placebo intervention**
  - Fasting safety labs (CBC, metabolic panel, transaminases, lipid panel, lipase)
  - Fasting leptin, soluble leptin receptor, insulin, cortisol, adiponectin, CRP, FGF21 levels
  - Physical exam
  - Standard measurements
  - VAS for nausea, satiety, hunger
  - 24-hr food recall
  - Assessment of symptoms, adverse events, and diet/medication compliance
  - Resting energy expenditure

- Mixed meal test
- Thermic effect of food (TEF) in subset of subjects
- Urine pregnancy test for premenopausal women
- **1, 3, and 6 month follow-up visits**
  - Standard measurements
- **5% Weight Loss Procedures**
  - Fasting lipid panel
  - Fasting leptin, soluble leptin receptor, insulin, cortisol, adiponectin, CRP, FGF21 levels
  - Standard measurements
  - VAS for nausea, satiety, hunger

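### Two sections make diet-arm follow-up to week 52 depend on undefined 'ongoing weight loss', contrary to the Overview and visit schedule; if applied, late diet-arm weights would be missing selectively

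*Combined protocol and SAP*

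**What the plan says.** All the relevant text is in the combined protocol and SAP.

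**Diet arm, conditional wording.** Rationale for study design: "Subjects in the dietary intervention arm will continue study participation for up to 52 weeks if they demonstrate ongoing weight loss". Study duration: "Subjects who demonstrate ongoing weight loss will continue placebo/dietary intervention for up to 52 weeks". Neither section defines the condition.

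**Exenatide arm.** Study duration: "Exenatide high responders will remain in the study even if weight loss plateaus or if there is weight regain".

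**Both arms, unconditional wording.** The Overview defines high responders to exenatide or placebo by at least 5% loss at week 12 and says "such subjects will remain in the study for 52 weeks with monthly study visits". It then gives one later exception, for placebo subjects below 10% loss at week 24, and ends with "At 52 weeks, high responders in both treatment groups will discontinue treatment". Study Visits places that exception in the week-24 visit: "Subjects who have not lost 10% body weight on placebo treatment discontinue participation at 24 weeks". The block headed "Weeks 28, 32, 36, 40, 44, 48 — Followup visits" contains no exit step and no check of continued loss.

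**Use of the late weights.** Outcome measurements compares exenatide responders with the "duration and magnitude of weight loss among subjects assigned to placebo with a calorie-restricted diet over 52 weeks", and also compares weight change 3 and 6 months after treatment or diet ends. Statistical methods defines a binary outcome, at least 1 kg further loss between weeks 12 and 52, and repeats its models in the diet group. Sample size calculation is built on the between-group difference in week 12 to 52 weight change.

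**The concern.** The authors foresaw plateau and regain and wrote an explicit retention sentence for one arm. For the other arm, two sections make staying in the study depend on continuing to lose weight. A diet woman who reached 10% by week 24 and then levelled off would leave under that wording, while an exenatide responder with the same course would be kept.

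Whether a week-52 weight exists would then depend, in the diet arm only, on the outcome itself. The diet women left at week 52 would be those still losing. Women who leave are described as ending participation, and no later weighing is planned for them. The statistical section gives no missing-data method. Investigators know the treatment arm, so the person interpreting an undefined criterion also knows to whom it applies.

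**Working it through.** **1. The plan's own figure.** Inputs from Sample size calculation: 38 and 18 women at week 52, difference 1 kg, SD 1.2 kg. Two-sided alpha of 0.05 is assumed, since that section gives none.

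- Standard error = 1.2 × √(1/38 + 1/18) = 0.343 kg
- 1 / 0.343 = 2.91
- Power = Φ(2.91 − 1.96) = 0.83, as stated (0.816 with the noncentral t)

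The calculation allows 50% diet-arm dropout (36 to 18). That covers lost numbers. It does not cover loss that depends on the outcome.

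**2. The rules side by side.**

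| Course | Rationale and Study duration, read literally | Overview and Study Visits |
|---|---|---|
| Exenatide, ≥5% at week 12, then plateau or regain | stays to week 52 | stays to week 52 |
| Diet, ≥5% at week 12, <10% at week 24 | leaves at week 24 (stated in Study duration) | leaves at week 24 |
| Diet, ≥10% at week 24, then plateau or regain | leaves, time unspecified | stays to week 52 |

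Only the last row conflicts, and it is the row that matters here.

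**3. Direction.** Under the literal rule the diet women who leave have less further loss than those who stay. The mean loss of those remaining is therefore at least the mean for all who qualified at week 24. The diet result is overstated and exenatide minus diet is understated. This holds for any rule that removes women for lack of further loss.

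**4. The 1 kg outcome.** Every woman who leaves has no value for it, and those missing are not simply the zeros. Assume a height of 1.60 m, so that BMI 28 and 50 correspond to 71.7 and 128 kg. A woman at exactly 5% at week 12 and 10% at week 24 has lost 5% of baseline in between, or 3.6 to 6.4 kg. She scores 0 only after regaining more than 2.6 to 5.4 kg. Many women who leave on a plateau would have scored 1. Selective loss is clear; the direction of bias in the regression coefficients is not.

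**5. Why no size can be given.** Let further loss after week 24 be Normal with mean m and SD s, and remove women with no net loss. The share removed is Φ(−m/s) and the overstatement is s·φ(m/s)/Φ(m/s). The documents give neither m nor s. Take s = 1.0 to 1.2 kg as an assumption: 1.2 is the plan's week 12 to 52 SD, and 1.2 × √(28/40) = 1.0.

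| m (kg) | Removed | Overstatement (kg) |
|---|---|---|
| 0 | 50% | 0.80–0.96 |
| 1 | 16–20% | 0.29–0.42 |
| 2 | 2–5% | 0.06–0.13 |
| 3 | 0.1–0.6% | 0.00–0.02 |

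Now change only the exit rule, to no net loss since week 12 among women who passed both cuts. Further assumptions are losses of 6% (SD 3%) by week 12 and 3% (SD 2%) in weeks 12 to 24, and later loss independent of earlier loss. At m = 0, simulation then removes 1.7–4.8% and the overstatement is about 0.1–0.2 kg instead of 0.80–0.96. These assumptions also imply a week 12 to 52 SD of about 1.6–2.5 kg, against the plan's 1.2. The answer follows the assumed rule and mean, not anything in the protocol.

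**The case against.** The strongest reply is that the operative text already settles the matter. In Study duration the phrase follows directly after the 5% and 10% stopping rules and can be read as their complement: women who do not fail continue. 'Up to' 52 weeks is explained by the week-24 exit. The Overview retains responders to either treatment with one stated exception, and no visit after week 24 contains a check. A third stopping rule would have no threshold, visit or procedure anywhere. The design figures are not in the extracted text and may confirm this.

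Much of this stands. A reader might infer from the exenatide-only sentence that diet women have no protection against removal for plateau. The documents do not support that, because the Overview protects responders in both arms subject to the week-24 rule. What remains is a conflict: no readable text equates 'ongoing weight loss' with the thresholds, and in ordinary usage a woman on a plateau is not showing it.

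Two points on consequence also stand. The week 12 to 52 mean difference is used for sizing, but Statistical methods specifies no test of it. The trajectory modelling would be less affected, since exit would depend on recorded weights, although late plateau or regain would be poorly observed in the diet group. The 52-week comparison in Outcome measurements and the 1 kg outcome still need the week-52 weight.

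**Conclusion.** The concern holds as an internal conflict with a conditional consequence. Two sections state a diet-only continuation condition that the Overview and visit schedule do not contain. If it is applied, week-52 diet weights, and possibly the 3- and 6-month weights, go missing according to outcome. The weight comparison is then biased towards diet, and the diet group's 1 kg outcome is selectively missing, with unpredictable effect on its coefficients.

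The size cannot be derived. It is zero if the phrase only restates the 5% and 10% thresholds. A reader might infer from the kilogram table that most of the planned 1 kg difference could disappear. That needs both a mean further diet loss near zero and one particular exit rule, and the documents support neither. Only the direction in the weight comparison should be carried forward, and only if the literal wording is followed.

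**What to change.** In Rationale for study design and Study duration, replace the 'ongoing weight loss' condition with having met the 5% threshold at week 12 and the 10% threshold at week 24. Add that these women remain to week 52 and the follow-up visits even if weight plateaus or is regained, as exenatide high responders do. If the diet intervention is nevertheless stopped early, still collect the scheduled weights, at least at week 52, and flag them as off-intervention in the analysis.

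The cost is wording in two sections, a few visits already on the schedule, and some diet-group weights taken off intervention. The change does not remove the separate selection created by the placebo-only 10% cut at week 24, which has no exenatide counterpart and needs its own consideration.

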### Recruiting and randomization:

The study will be advertised in local print media and on the radio, and flyers will be posted in Boston, including the Longwood Medical Area. The study will also be advertised via the internet with clinicaltrials.gov, TrialX, and on CraigsList. Participants may also be referred for participation by their primary care physicians or

endocrinologists. Individuals who respond to advertisements will first have a brief telephone screen, which will include questions about past medical history, medication use and the ability to travel to Boston for study visits. Subjects who have been deemed appropriate for enrollment after a telephone screen will be scheduled for a screening visit. After they have completed the screening visit, and once the results of all of their screening labs have been reviewed, they will be asked to enroll in the study. If they agree to enroll, they will now be randomized in a 2:1 ratio to the exenatide treatment arm or placebo/diet treatment arm of the study, respectively. The research pharmacy at the Beth Israel Deaconess Medical Center will randomize patients and allocate exenatide or placebo to subjects in the at the enrollment visit.

**Study duration:**

All subjects randomized to exenatide treatment will continue participation for 12 weeks. At 12 weeks, subjects who are high responders will continue participation for 52 weeks plus followup visits at 3 and 6 months. Exenatide high responders will remain in the study even if weight loss plateaus or if there is weight regain. Exenatide nonresponders will discontinue participation after 12 weeks.

Subjects in the placebo/diet intervention arm will discontinue participation if they fail to lose 5% of their body weight after 12 weeks or 10% of their body weight after 24 weeks. Subjects who demonstrate ongoing weight loss will continue placebo/dietary intervention for up to 52 weeks, plus follow-up visits at 3 and 6 months. Metabolic monitoring will occur when subjects have lost 5% and 10% of their body weight.

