**Explanations of measurements and assessments:**

*Labs for exenatide and diet interventions:* The placebo of this study allows us to compare metabolic changes that occur with exenatide versus diet-induced weight loss. We are particularly interested in the 5% and 10% weight loss timepoints and will measure metabolic parameters when that degree of weight loss is achieved. However, the 5%, 10%, 15%, and > 15% weight loss metabolic visits will not be scheduled within 2 weeks of starting the treatment, as acute weight loss within this time frame is likely due to fluid shifts rather than fat loss.

*Bioelectrical impedance:* Bioelectric impedance analysis (BIA) measures the opposition of bodily tissues to the flow of a mild (less than one milliAmp) alternating electric current (Gudivaka et al., 1999). Impedance is a function of two components (vectors): the resistance of the tissues themselves and the additional opposition (reactance) due to the capacitant effect of membranes, tissue interfaces, and nonionic tissues. Electrodes are typically placed on a wrist and an ankle and change in voltage between electrodes is measured. RJL system Quantum II Bioelectrical Body Composition Analyzer Testing using Cyprus software will be used in this study. The subject is generally tested using the right arm and foot. She will be in a supine position with arms 30 degrees from the body and legs not touching. The testing time takes less than 2 minutes and results are immediately available from software program. Resistance and reactance are used to calculate % body fat (Kotler et al., 1996).

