To estimate the number and shape of the weight loss trajectories, we will use a mixture modeling technique of the longitudinal data of monthly weights for each subject. We will first plot the data for each subject over time. The graphs will allow us to have some understanding of the shape of the observed trajectories, and how the curves cluster. We will assume that the number of clusters ranges from one to six, but we expect the optimal estimate of the number of clusters is three or four, as described above, with the largest cluster consisting of trajectory of shape T1. The marginal density of a subject having weight measurement at a particular time point is modeled as a function of the product of two densities: the probability of the weight measurement belonging to a particular group, and the probability of observing such a measurement conditioning on the particular group. The first probability is modeled using a generalized logit model since the outcome is categorical (from 1 to 6 categories/types of trajectories), and the second probability is a polynomial linear regression of the weight measurement as a function of time (linear, quadratic, cubic). To select the optimal number of trajectories, we will compare the Bayesian Information Criteria (BIC) value from the six models (corresponding to 1 to 6 types of trajectories). The algorithm and the SAS macro for this type of modeling has been published (Jones 2007). We will repeat the modeling technique above for group B in order to assess the number and shapes of the trajectories in this group.

For aim 2, we will first create a binary outcome variable. The outcome is 1 if the weight loss difference between 12-week and 52-week is at least 1 kg; otherwise, it is 0. We will perform multivariable logistic regression to assess the association between metabolic parameters and this outcome. We consider the association to be statistically significant if the p-value is less than 0.05, and the overall model c-statistic is above 0.8. Once these metabolic parameters have been identified and quantified, we will also use the result from the trajectory analysis (aim 1) to assess the distribution of the metabolic parameters across different trajectories. We will model the likelihood of falling into a particular trajectory as a function of metabolic parameters (i.e. the change in a particular metabolic parameter may affect a certain trajectory but not all trajectories of weight loss).

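### Only diet women must reach 10% loss at week 24 to stay, so a week 12-to-52 comparison of the women left selects group B alone on part of its outcome; no correction is stated and the direction is unknown

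*Combined protocol and SAP*

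**What the plan says.** All references are to the combined protocol and SAP.

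- **Both arms, week 12.** Women below 5% loss leave the study (Overview; Study Visits).
- **Diet arm, week 24.** The Overview says "At 24 weeks, subjects in the placebo group who have not lost 10% of their body weight will discontinue participation". The week-24 visit list repeats it ("Subjects who have not lost 10% body weight on placebo treatment discontinue participation at 24 weeks"), and so does Study duration.
- **Diet arm, continuation.** Rationale for study design adds that these women "will continue study participation for up to 52 weeks if they demonstrate ongoing weight loss", without defining the phrase.
- **Exenatide arm.** Study duration says "Exenatide high responders will remain in the study even if weight loss plateaus or if there is weight regain".
- **Weight comparison.** Outcome measurements promises a comparison of the size and duration of weight loss between arms over 52 weeks. Sample size calculation is built on the A-minus-B difference in weight change from week 12 to week 52: 1 kg, SD 1.2 kg, 38 and 18 women remaining, power 0.83. It allows for 25% dropout in A and 50% in B.
- **Models.** Statistical methods describes a "mixture modeling technique of the longitudinal data of monthly weights for each subject" for group A, then says "We will repeat the modeling technique above for group B". Aim 2 dichotomises the week 12-to-52 change at 1 kg and reads the A-B difference in coefficients as a possible exenatide effect.

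No section gives a missing-data method, a weighting scheme, follow-up weights after a week-24 removal, or a sensitivity analysis for it.

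**The concern.** Week 24 lies inside the week 12-to-52 interval. A diet woman's loss from week 12 to 24 helps decide whether she is retained, and it also counts towards the outcome on which the retained women are compared. An exenatide woman with the same weight course is retained whatever it is. Even if the two arms had identical true courses, the women left in B could differ from those left in A in mean loss after week 12. That difference would come from the retention rule and would be read as treatment. At stake are the size of the A-B difference, the stated power, and the error rate of any test of it.

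**Working it through.** **1. The plan's own figure.** Inputs from Sample size calculation: n = 38 and 18, SD 1.2 kg, difference 1 kg. A two-sided 5% level is assumed, because that paragraph states none.

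SE = 1.2 × √(1/38 + 1/18) = 0.343 kg. 1/0.343 − 1.96 = 0.95, so power is 0.83 (0.82 with the t distribution). The figure reproduces. It assumes that the contrast carries no selection shift.

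**2. Closed form for the shift.** Suppose a fraction k of diet responders passes week 24, and total loss at week 24 has correlation ρ with week 12-to-52 loss. The mean loss in B then moves by [φ(z)/k] × ρ × 1.2 kg, where φ is the standard normal density and z the cut-off that leaves the fraction k above it. The documents give neither k nor ρ.

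- k = 0.50, ρ = +0.3: (0.399/0.50) × 0.3 × 1.2 = 0.29 kg more loss in B. A true 1 kg difference shows as 0.71 kg, with power 0.55.
- k = 0.50, ρ = −0.3: 0.29 kg less loss in B. A true 1 kg shows as 1.29 kg, with power 0.96.
- k = 0.75, ρ = ±0.3: 0.15 kg either way, with power 0.69 or 0.92.

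**3. Simulation with identical true courses in both arms.** Assumed, because the documents do not say: 95 kg start; week-12 loss normal with mean 6–8% and SD 2.5%, truncated at 5%; a further 2–3% by week 24; 40–60% of the week 12-to-52 variance arising by week 24. The overall SD is held at the protocol's 1.2 kg. There were 27 scenarios per cell with 400,000 women each; the 18 with a pass rate of at least 50% are shown. Entries are the shift in B's mean loss in kg. Positive counts against exenatide, negative in its favour.

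| Correlation of week-12 loss with week 12–24 loss | No link of week-24 loss to later loss | Link −0.3 | Link −0.5 |
|---|---|---|---|
| 0 | 0.13 to 0.35 | −0.02 to 0.15 | −0.19 to −0.02 |
| −0.3 | 0.04 to 0.20 | −0.16 to 0.03 | −0.28 to −0.07 |
| −0.6 | −0.13 to 0.02 | −0.30 to −0.08 | −0.40 to −0.12 |

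A differently built simulation, with 45–50% passing and 30% of excess loss regained after week 24, gave 0.20 to 0.39 kg in favour of exenatide.

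**4. Consequence at the two ends**, keeping SE = 0.343 kg.

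- 0.35 kg against: a true 1 kg shows as 0.65 kg. 0.65/0.343 − 1.96 = −0.07, so power is 0.47. With no true difference the test rejects about 17% of the time.
- 0.40 kg in favour: with no true difference the test rejects about 21% of the time (0.40/0.343 − 1.96 = −0.79). The apparent power of 0.98 for a true 1 kg is partly artefact.

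**5. Does using the recorded weights help?** In every scenario of the table, B's week 12-to-52 change was estimated for all its week-12 responders, conditioning on week-12 and week-24 weights. The remaining bias was within 0.01 kg.

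**The case against.** **The rule has a purpose.** The diet arm exists as a weight-loss comparator, and the protocol says "We are particularly interested in the 5% and 10% weight loss timepoints". That is a reasonable basis for a metabolic comparison at matched loss. It does not make an unadjusted comparison of week 12-to-52 weight fair. The comparator rationale itself is given only for the 5% rule at week 12.

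**No test is named.** This stands. Statistical methods specifies no A-minus-B test of the week 12-to-52 change. The trajectory model states no completer restriction and may use weights recorded before removal, but it is fitted to each group separately and gives no A-minus-B estimate. The sizes above therefore apply to the completer comparison that the sample size implies.

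**The contrast was never randomised.** This also stands. Both arms are already selected at week 12 and follow different diets. The week-24 rule adds a further selection in one arm only.

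**The dropout allowance covers it.** The 50% allowance for B reduces the number analysed. It does not address which women are removed, and the documents do not say how much of it is due to the 10% rule.

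**Stronger readings a reader might infer.**

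- *The rule is biased against exenatide.* The documents do not support a direction. The background section itself says that diet-induced loss lowers resting energy expenditure and so facilitates regain. Enough regain among large early losers reverses the sign.
- *Ongoing weight loss is a second, continuing removal rule.* In Study duration the phrase directly follows the 5% and 10% thresholds and may only paraphrase them. The visit lists for weeks 28 to 48 show no further removal.
- *Aim 2 is seriously distorted.* With 18 women in B, any distortion is small beside sampling error, and the secondary objective concerns response to exenatide.

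**Conclusion.** The point holds, and should be fixed. It is certain from the text that retention after week 12 differs by arm, that the week-24 criterion overlaps the week 12-to-52 outcome, and that no correction is stated. The size and sign are not known. Under the inputs listed, the shift runs from about 0.35 kg against exenatide (early and later loss uncorrelated, no regain link) to about 0.4 kg in its favour (larger early losers lose less or regain later). Both ends are material against a 1 kg target. Both depend on assumed correlations and on a pass rate of at least half at week 24. The arithmetic behind the power of 0.83 is right. What it lacks is support for assuming no selection shift. Confidence is high on the structure and medium on the importance.

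**What to change.** Leave the participation rules as they are and change the analysis.

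1. Make the A-B weight comparison one pooled likelihood repeated-measures model from week 12 to week 52, with arm-by-visit means and week-12 loss as covariate. Include every woman in either arm with at least 5% loss at week 12 and every recorded weight, including those up to and including week 24 from diet women then removed. The ten visits from week 16 to week 52 need 10 × 11/2 = 55 unstructured covariance parameters, so name a fallback now: for example heterogeneous Toeplitz, then random intercept and slope with a knot at week 24. State whether slopes are common to the arms or arm-specific.
2. Report the week 12-to-24 contrast, which precedes the unequal filter, as a supporting result.
3. As a sensitivity analysis, apply the 10% week-24 criterion analytically to both arms. In simulation this gave 0.92–1.08 kg for a true 1 kg.
4. State that week-52 values for removed diet women are model-based under missing at random, and that the result compares responders with responders under different diets and is not a randomised effect.
5. In aim 2, add week-12 loss as a covariate, and do not read the A-B coefficient difference as an exenatide effect without the same caveat.

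**Cost.** SAP wording, one model and one covariate, on weights the protocol already collects. The price is precision, and reliance on the model after week 24 for the women removed. With 50 responders in A and 36, 27, 22 or 19 in B, and early and later loss uncorrelated, the simulated SE at a 54% pass rate was 0.32, 0.35, 0.38 and 0.39 kg with common slopes, and 0.38, 0.44, 0.50 and 0.54 kg with arm-specific slopes. The completer formula in the plan gives 0.343 kg. At a correlation of −0.3 with arm-specific slopes there was no gain in power, only less bias.

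The number of diet responders decides this, and the sponsor can count it. The protocol reports 28 + 10 = 38 placebo women by 6/5/15, reading the 10 as additional. If 50–70% reached 5% (assumed), that is 19–27. If enrolment reached 250 at 2:1, the 250 − 146 = 104 further women would bring placebo to about 38 + 35 = 73, or 36–51 responders on the same assumption.
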